### Design

TICO is a master protocol to evaluate the safety and efficacy of multiple investigational agents aimed at modifying the host immune response to severe acute respiratory syndrome coronavirus 2 (SARS-CoV-2) infection, or directly enhancing viral control in order to limit disease progression.

Trials within this protocol will be adaptive, randomized, blinded and initially placebo-controlled. Participants will receive standard of care (SOC) treatment as part of this protocol. If an investigational agent shows superiority over placebo, SOC for the study of future investigational agents may be modified accordingly.

The protocol is for a phase III randomized, blinded, controlled platform trial that allows investigational agents to be added and dropped during the course of the study for efficient testing of new agents against control (i.e., placebo + SOC) within the same trial infrastructure. When more than one agent is being tested concurrently, participants will be randomly allocated across agents (as well as between the agent and its placebo). For analysis, placebo groups of concurrently randomized agents will be pooled; therefore, control groups may overlap for different agents.

Randomization will be stratified by study site pharmacy and disease severity. There are 2 disease severity strata, defined as below:

- **Disease severity stratum 1:** Absence of all of the following: stroke, meningitis, encephalitis, myelitis, myocardial infarction, myocarditis, pericarditis, symptomatic congestive heart failure (NYHA class III or IV), arterial or deep venous thrombosis or pulmonary embolism, requirement for invasive mechanical ventilation, ECMO, mechanical circulatory support, vasopressor therapy, or new renal replacement therapy.
- **Disease severity stratum 2:** Presence of at least one of the excluded conditions or treatments in disease severity stratum 1.

The **primary endpoint** is the time from randomization to sustained recovery, defined as being discharged from the index hospitalization, followed by being alive and home for 14 consecutive days prior to Day 90. The definition of home will be operationalized as the level of residence or facility where the participant was residing prior to hospital admission leading to enrollment in this protocol.

An independent Data and Safety Monitoring Board (DSMB) will regularly review interim analyses that summarize safety and efficacy outcomes. For any agent, at the outset of the

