For time-to-event analyses, if strata are too small for fitting separate baseline hazard functions, strata may be added as a categorical covariate to models instead. Whenever possible, however, analyses should be stratified by disease severity (with separate baseline hazard functions).

For **binary outcomes**, probabilities will be compared between the investigational agent and its control group using Cochran-Mantel-Haenszel tests (CMH) or logistic regression. If the numbers are sufficiently large, CMH tests will be stratified according to the planned randomization strata (disease severity and site pharmacy), as described above under “stratification”. Odds ratios (OR) with 2-sided 95% confidence intervals (CI) will be estimated using logistic regression models.

For longitudinally measured binary outcomes, the treatment effect through follow-up will be estimated with 95% confidence intervals using generalized estimating equations (GEE) with a logit link function; the treatment effect is estimated via the interaction between the indicator for treatment group and the indicator for follow-up (versus baseline) visits. When there is more than one follow-up visit, “visit number” (day) may be included as categorical variable in the model, for variance reduction; alternatively, “time” may be included as a continuous variable.

**Ordered categorical outcomes (pulmonary and pulmonary+)** will be compared between treatment groups using proportional odds models, and the summary OR will be estimated with a 2-sided 95% CI. Additionally, to aid the interpretation, the ordinal outcome will be dichotomized according to cumulative probabilities of the ordered categories, comparing treatment groups for proportions of participants in category 1, in the “best 2 categories”, “best 3 categories”, etc.; these comparisons will be performed using logistic regression (or stratified CMH tests).

For interim analyses of the ordinal outcomes, if one or more recently enrolled participants have died (i.e., their outcome status is known) but their current administrative follow-up has not yet reached the time point at which the treatment groups are to be compared (e.g., day 5), analyses will be restricted to participants with administrative follow-up greater or equal to the target time point.

Models will be adjusted for the baseline categories of the pulmonary+ outcome and for study pharmacy, by including the corresponding indicator variables in the model.

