### 8.3 Other Secondary Outcomes

The protocol defines a number of secondary endpoints in addition to the two key endpoints described in section 8.2 above. These analyses will be carried out for the final report. Selected secondary endpoints may also be analyzed for interim monitoring reports, to help evaluate the safety and efficacy of the investigational agent.

Below, the secondary outcomes from section 4.2.2 of the protocol are cited, with a short description of the analysis methods. For each outcome, the treatment group comparisons will be stratified by disease severity at study entry and by site pharmacy, as described in section 3 under “stratification”.

- Time to discharge for the initial hospitalization. Treatment groups will be compared using time-to-event methods that take into account the competing risk of death, similar to the analyses for time to sustained recovery described in section 8.1.
  - Hospital readmissions will be summarized using methods for recurrent events (i.e. those who are readmitted will re-enter the risk set).
- Days alive outside of a short-term acute care hospital up to day 90. For this analysis, the “last-off” method will be used, i.e., days from the latest hospital discharge to day 90 will be counted. A person who dies within 90 days will be assigned a value of 0, consistent with the approach taken in trials of intensive care-based interventions. We will present

the median days by group and test the hypothesis of no difference between arms with a Wilcoxon rank sum test.

- For interim analyses, only participants who have reached Day 90 (administrative follow-up for those who died) will be included, to avoid bias. Alternatively, a shorter time period may be used.
- Pulmonary+ and pulmonary ordinal outcomes on Days 1-7, and the pulmonary ordinal outcome on Days 14 and 28. The proportion of participants in each category of the pulmonary and pulmonary+ outcomes will be summarized over time (both outcomes at days 1-7, the pulmonary outcome also at Days 14 and 28); at each of those days, treatment groups will be compared using proportional odds models as described in section 3; the proportional odds models will be adjusted for the categories of the pulmonary+ outcome at baseline and for study site pharmacy. If participants in both disease severity strata are enrolled, the models will also be adjusted for the interaction between disease severity stratum and pharmacy.

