Subgroup analyses for the **composite safety endpoint at Day 5** will use logistic regression, stratified by disease severity at study entry. Within each subgroup, the number and percent of participants with events will be calculated by treatment group, and ORs with 95% CIs comparing the investigational agent versus control will be estimated. Global tests for heterogeneity of the treatment effect across subgroups will be carried out, by testing for interactions between the treatment group and the subgroup variable in an expanded model, as described above. Additionally, subgroup analyses for the composite safety endpoint **through Day 5** will be conducted using Cox proportional hazards models, stratified by disease severity.

Subgroup analyses for **all-cause mortality** and **safety endpoints** that are analyzed using time-to-event methods (through Day 5, Day 28 and through Day 90) will use stratified Cox proportional hazards models, since death is part of the composite endpoints and not a competing risk. HRs will be estimated with 95% CIs for each subgroup, and global tests of heterogeneity of the treatment effect will be carried out, as described above. The proportional hazards models will be stratified by disease severity.

Subgroup analyses for the **pulmonary** and pulmonary+ ordinal outcomes on Day 5 will use proportional odds models, adjusted for the pulmonary or pulmonary+ category at study entry. In order to summarize the distributions across the categories of the ordinal outcome, the mean score (using 1-7 for best to worst) will be calculated by treatment group within each subgroup. For each subgroup, summary ORs with 95% CIs will be calculated. Global tests for heterogeneity of the treatment effect across subgroups will be carried out, as described above.

Subgroup analyses for **time to discharge from the index hospitalization** will use the Fine-Gray model (with death as competing risk), stratified by disease severity at study entry. Similar analyses as described above for time to sustained recovery will be carried out.

Additionally, subgroup analyses will be conducted for subgroups formed by a disease progression risk score at baseline. The construction of this risk score has been published and will be revisited as data on the sustained recovery endpoint accumulate for new investigational agents.

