#### Monitoring boundary for harm:

- Until the first 300 participants are enrolled (150 per study arm) and the early futility analysis is conducted, the treatment groups will also be compared for the “pulmonary” and “pulmonary+” ordinal outcomes at Day 5, using a proportional odds model stratified by study pharmacy and pulmonary+ outcome category at baseline. A Haybittle-Peto boundary with 2.5 standard deviation (SD) for the first 50 participants enrolled and 2.0 SD afterwards will be used as a guideline for harm.
- After the study population is expanded to include disease severity stratum 2, these analyses are performed by disease severity stratum.

At the discretion of the DSMB, these safety reports will be prepared at a frequency they specify, for example, weekly. The DSMB may also request additional data summaries.

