- Supplemental oxygen  $\geq 4$  L/min (or  $\geq 4$  L/min above premorbid requirements, but not high-flow oxygen) (pulmonary+ category 4)

- To supplement the overall summary odds ratios for the 7-category outcomes, each dichotomized definition of improvement that can be formulated from the components of the ordinal outcomes will be considered separately; for example, treatment groups will be compared for the proportions of participants in category 1 on Day 5, proportions in categories 1 or 2 (“best two categories”), in categories 1-3, etc. Proportions will be tabulated, and odds ratios for active versus control groups will be estimated with 2-sided 95% CIs using logistic regression models. These analyses need to be interpreted with caution, because they are not adjusted for inflation of type I error due to multiple comparisons.
- Subgroup analyses will be carried out for the Pulmonary and Pulmonary+ outcomes on Day 5, to supplement the early futility analyses. The goal is to determine whether the treatment effect differs across subgroups, and to aid the DSMB in considerations on whether there are safety concerns in specific subgroups. Principles for subgroup analyses are described in section 9.1; here, subgroup analyses are based on the proportional odds models. In particular, heterogeneity of the treatment effect across the baseline pulmonary+ categories will be assessed.
- After an investigational agent has passed initial futility assessment and enrollment has been expanded to include participants in disease severity stratum 2, treatment comparisons for the pulmonary and pulmonary+ outcomes on Day 5 continue, and will be performed separately for each of the two disease severity strata, to assess safety for the more severely ill participants in stratum 2.

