## Appendix A. Definition of the Pulmonary and Pulmonary+ ordered categorical outcomes

The Pulmonary categorical outcome is primarily defined based on oxygen requirements. The categories of the Pulmonary+ outcome are similar, except that categories 4 and 5 also capture selected extra-pulmonary complications, highlighted in red below.

Pulmonary outcome	Pulmonary+ outcome
1. Can independently undertake usual activities with minimal or no symptoms	1. Can independently undertake usual activities with minimal or no symptoms
2. Symptomatic and currently unable to independently undertake usual activities but no need of supplemental oxygen (or not above premorbid requirements)	2. Symptomatic and currently unable to independently undertake usual activities but no need of supplemental oxygen (or not above premorbid requirements)
3. Supplemental oxygen (<4 liters/min, or <4 liters/min above premorbid requirements)	3. Supplemental oxygen (<4 liters/min, or <4 liters/min above premorbid requirements)
4. Supplemental oxygen ( $\geq 4$ liters/min, or $\geq 4$ liters/min above premorbid requirements, but not high-flow oxygen)	4. Supplemental oxygen ( $\geq 4$ liters/min, or $\geq 4$ liters/min above premorbid requirements, but not high-flow oxygen) or any of the following: stroke (NIH Stroke Scale [NIHSS] <math>\leq 14</math>), meningitis, encephalitis, myelitis, myocardial infarction, myocarditis, pericarditis, new onset CHF NYHA class III or IV or worsening to class III or IV, arterial or deep venous thromboembolic events
5. Non-invasive ventilation or high-flow oxygen	5. Non-invasive ventilation or high-flow oxygen, or signs and symptoms of an acute stroke (NIHSS >14)
6. Invasive ventilation, extracorporeal membrane oxygenation (ECMO), mechanical circulatory support, or new receipt of renal replacement therapy	6. Invasive ventilation, ECMO, mechanical circulatory support, new receipt of renal replacement therapy, or vasopressor therapy
7. Death	7. Death

The term “usual activities”, in categories 1 and 2 for both outcomes, refers to activities of daily living that the participant was able to undertake prior to the current illness.

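### In severity stratum 2, the baseline pulmonary+ covariate adjusts the Day 5 ordinal models only partly for oxygen need; baseline oxygen category should be added

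*SAP*

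**What the plan says.** The adjustment rule appears four times in the SAP.

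- Section 3, for ordered categorical outcomes: "Models will be adjusted for the baseline categories of the pulmonary+ outcome and for study pharmacy".
- Section 8.3, for the daily secondary analyses: "the proportional odds models will be adjusted for the categories of the pulmonary+ outcome at baseline and for study site pharmacy". When both strata are enrolled, a severity-by-pharmacy interaction is added, but no oxygen term.
- Section 10.1, for the harm guideline: "using a proportional odds model stratified by study pharmacy and pulmonary+ outcome category at baseline". It continues: "After the study population is expanded to include disease severity stratum 2, these analyses are performed by disease severity stratum".
- Section 10.2.2 uses the same covariates for the Day 5 outcomes. After expansion, the comparisons "will be performed separately for each of the two disease severity strata", for the stated purpose of assessing safety in the sicker stratum.

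Section 1.2 defines stratum 2 as "Presence of at least one of the excluded conditions or treatments in disease severity stratum 1". In Appendix A, pulmonary+ category 4 is oxygen at ≥4 L/min or any of a list of events that includes "meningitis, encephalitis, myelitis, myocardial infarction, myocarditis, pericarditis, new onset CHF NYHA class III or IV or worsening to class III or IV".

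Section 10.2.2 states that adjusting for pulmonary+ is the same as adjusting for oxygen category, but only while eligibility is restricted to stratum 1. The Day 5 subgroup models in section 9.1 are worded differently: "adjusted for the pulmonary or pulmonary+ category at study entry".

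**The concern.** A baseline covariate helps an ordinal comparison to the extent that it predicts the outcome. For the pulmonary outcome the natural choice is the same scale at baseline, which the trial records. In stratum 2 the plan uses pulmonary+ instead, and category 4 of that scale no longer says how much oxygen the participant needs.

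This affects the separate Day 5 comparison in stratum 2 and the harm guideline applied by stratum. A coarser covariate makes harm or benefit somewhat harder to see there. It also pulls the conditional odds ratio toward 1 and leaves part of any chance imbalance in oxygen need uncorrected.

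Elsewhere the SAP uses the outcome's own baseline. The risk score in section 13.2 models the Day 5 pulmonary outcome from the baseline pulmonary category, and section 3 adjusts continuous outcomes for their own baseline value.

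**Working it through.** **1. The plan's own figure.** Section 1.4 gives 95% power for N = 300, OR 1.60, one-sided α = 0.30. The formula for ordered categories is N = 12(z_α + z_β)² / [ln(OR)² (1 − Σp³)]. With z = 0.5244 and 1.6449, 12 × 2.1693² / 0.4700² = 255.6. So N = 300 is exact when 1 − Σp³ = 0.852. The control distribution is not in the documents; over a range of assumed ones, power at N = 300 is 94.0% to 96.4%. The figure reproduces. It concerns stratum 1, so the present point does not touch it.

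**2. What the scales do in stratum 2** (section 1.2 against Appendix A).

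| Baseline state | Pulmonary | Pulmonary+ |
|---|---|---|
| Listed category 4 event, room air | 2 | 4 |
| Same, <4 L/min | 3 | 4 |
| Same, ≥4 L/min | 4 | 4 |
| Same, high-flow or non-invasive ventilation | 5 | 5 |
| Invasive ventilation or ECMO | 6 | 6 |
| Stable NYHA III/IV heart failure only | by oxygen | by oxygen |

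The first three rows merge and the others do not. The last row arises because stratum 2 takes any symptomatic class III/IV failure, whereas category 4 requires new onset or worsening.

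**3. How much is lost.** Assume stratum 2 shares of (pulmonary 2–4 with a category 4 event / 5 / 6) of 80/10/10, 50/20/30 and 25/25/50, with 2–4 split equally. The variance inside the merged category is 2/3 times its share. For 80/10/10 the total variance is 13.833 − 3.5² = 1.583, so the part kept is 1 − 0.533/1.583 = 66%. The other mixes keep 84% and 90%.

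**4. Effect on the test.** Simulation: N = 150 in stratum 2, 1,500 runs per cell, proportional odds fits, both models fitted to the same data, no pharmacy term. The slope is the log-odds per baseline pulmonary step. In this set-up pulmonary+ is a function of the pulmonary category, so adding the pulmonary category and substituting it give the same model. Information ratio = [(mean log OR / mean SE), full ÷ current]².

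| Mix | Slope | Power, OR 1.6 (two-sided 5%) | P(Z < −2), OR 1/1.6 | Information ratio (benefit; harm) |
|---|---|---|---|---|
| 80/10/10 | 0.5 | 35.0% → 37.2% | 34.3% → 35.7% | 1.05; 1.04 |
| 80/10/10 | 1.0 | 29.5% → 33.7% | 32.8% → 37.9% | 1.20; 1.19 |
| 50/20/30 | 0.5 | 36.4% → 36.9% | 35.1% → 36.1% | 1.04; 1.03 |
| 50/20/30 | 1.0 | 33.2% → 36.1% | 33.1% → 36.5% | 1.11; 1.14 |
| 25/25/50 | 0.5 | 37.0% → 37.7% | 34.5% → 35.2% | 1.01; 1.02 |
| 25/25/50 | 1.0 | 35.3% → 36.7% | 35.3% → 36.6% | 1.03; 1.04 |

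Example, 80/10/10, slope 1.0, OR 1.6: (0.462/0.302)² / (0.414/0.297)² = 1.20. The mean estimate moves from exp(0.414) = 1.51 to exp(0.462) = 1.59.

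At OR 1, two-sided rejection is 4.7–6.4% under the current model and 5.1–6.4% under the full one. P(Z < −2) is 2.1–2.9% and 1.9–2.7%. There is no detectable change in error rate.

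**5. Larger stratum, steeper slopes.** With N = 300, OR 1.8, baseline shares for pulmonary 2 to 6 of (.25, .25, .20, .15, .15) or (.15, .15, .15, .20, .35), and slopes 0.8, 1.2 and 1.6, power moves 80 → 83%, 72 → 81% and 65 → 78% in the first mix, and 78 → 79%, 73 → 79% and 72 → 79% in the second. The largest gain, 13 points, corresponds to (0.772 + 1.960)² / (0.385 + 1.960)² = 1.36.

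**6. Add or substitute?** Baseline vasopressor use and stroke with NIHSS >14 raise pulmonary+ but not pulmonary, so substitution discards them. In the same N = 300 mixes with slopes 0.5 and 0.8, suppose vasopressor use also predicts Day 5 status. Substitution then gives an information ratio of 0.94–1.05 (20% on vasopressors, log-odds 1.5) and 0.84–0.96 (30%, log-odds 2). In a further comparison of the two options over a common set of settings, substitution gave 0.93–1.26 and addition 1.03–1.26. Addition never lost information.

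**The case against.** The strongest reply has four parts.

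First, ventilatory support is still captured and treatment is randomized, so nothing is invalid. The smaller odds ratio is non-collapsibility under coarser conditioning, not bias in assignment. This stands, and it limits the point to precision.

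Second, a reader might infer that oxygen need is wholly unadjusted in stratum 2, or that the efficacy decision is weakened. The documents do not support either. Categories 5 and 6 remain separate. The futility rule uses stratum 1 only. Section 10.2.2 calls the stratum 2 comparison a safety assessment, and the section 10.3 boundaries rest on sustained recovery. Stratum 2 safety also draws on the composite outcomes, mortality and organ failure in section 7.

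Third, the plan covers some of this already: section 9.1 has subgroup analyses by baseline oxygen category, and its wording of the subgroup covariate is permissive rather than contradictory. That is fair, but subgroup estimates do not replace adjustment in the stratum 2 comparison itself.

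Fourth, replacing pulmonary+ with pulmonary can lose information. This stands, and it is why the covariate should be added and not substituted.

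**Conclusion.** The gap is real and modest. For stratum 2 participants with a listed category 4 event, the specified covariate does not separate room air, <4 L/min and ≥4 L/min, so the Day 5 models adjust for baseline oxygen need only in part. The consequence is lost precision and an attenuated conditional odds ratio in the stratum 2 safety comparison. It does not inflate type I error and does not change stratum 1 or the futility gate.

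Full adjustment adds about 3% to 26% information in nearly all settings tried. The weakest cells are near 1–2% and one steep setting reaches 36%. Power gains run from roughly zero to 13 points, with the top of that range from the steepest slope. These are illustrations and not bounds: stratum 2 size, oxygen mix and baseline effect are all assumed. The simulations also place every non-ventilated stratum 2 participant in category 4, which ignores stable heart failure and so overstates the merging.

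Practical reach depends on enrolment. AZD7442 randomized nobody in stratum 2 (Appendix E-5), and the documents do not state the number for other agents. The SAP is a platform plan, so the rule should still be right for an agent that does expand.

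**What to change.** In SAP sections 3, 8.3, 10.1 and 10.2.2, add a rule along these lines: whenever an analysis includes stratum 2 participants, the models for both ordinal outcomes include the baseline pulmonary+ category and, in addition, the baseline oxygen (pulmonary) category, with redundant indicators dropped. Use the same rule in section 9.1 in place of the either/or wording. Section 3 favours pulmonary+ over pharmacy when data are sparse; say there where the oxygen term ranks.

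Do not replace pulmonary+ with pulmonary, which would remove baseline vasopressor use and severe stroke from the pulmonary model.

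The cost is SAP wording and about two to four extra indicator terms. The data are already collected: section 5 and Table D-1 list both scales at baseline. Stratum 1 analyses do not change, because the two scales coincide there.
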